8.2 Imaging Core Laboratory

An imaging protocol will be provided to the site. The imaging core laboratory will be responsible for the qualitative image analysis to determine aneurysm characteristics, side branch coverage by the Pipeline device, aneurysm occlusion, parent artery stenosis, and device migration.

[figure not shown]

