21 DEFINITIONS

TERM	DEFINITION
Adverse Event (AE)	
Any untoward medical occurrence, unintended disease or injury, or untoward clinical signs (including abnormal laboratory findings) in subjects, users or other persons, whether or not related to the investigational medical device. (ISO 14155:2011 3.2)
 
Note 1: This definition includes events related to the investigational medical device or the comparator.
 
Note 2: This definition includes events related to the procedures involved.
 
Note 3: For users or other persons, this definition is restricted to events related to investigational medical devices.

Adverse Device Effect (ADE)	
An adverse event related to the use of an investigational medical device. (ISO 14155:2011 3.1)
 
Note 1: This definition includes adverse events resulting from insufficient or inadequate instructions for use, deployment, implantation, installation, or operation, or any malfunction of the investigational medical device.
 
Note 2: This definition includes any event resulting from use error or from intentional misuse of the investigational medical device.

Device Migration	
Movement of one or more Pipeline™ Flex Embolization Device with Shield Technology™ of more than 5 mm in its parent artery location in comparison to the post-placement angiogram.

Device-related Adverse Effect	
Event has a strong temporal relationship to the study device, and alternative etiology is less likely.

TERM	DEFINITION
Procedure	The primary study procedure involving the placement of the Pipeline™ Flex Embolization Device with Shield Technology™ at Day 0.
Neurological Adverse Event	An adverse event with an underlying neurological cause.
Neurological Death	Subject death due to neurologic reasons.
Point of Enrollment	Once the subject has signed and dated the Informed Consent or DRF, point at which the Pipeline™ Flex Embolization Device with Shield Technology™ is advanced into the micro catheter inside the subject.
Procedure-related Adverse Event	Event has a strong temporal relationship to the procedure (Day 0). This includes AEs attributable to any device(s) other than the Pipeline™ device used at procedure (Day 0), such as access devices, delivery microcatheters, non-ionic contrast, guidewires, or any other adjunctive, approved/cleared device for treatment of intracranial aneurysms.
Retreatment	Any subsequent intervention (post study procedure with Pipeline implant) performed to treat the target IA.

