mRS	Modified Rankin Score	Scale for measuring general neurological function. 0 No symptoms at all 1 No significant disability despite symptoms; able to carry out all usual duties and activities 2 Slight disability; unable to carry out all previous activities, but able to look after own affairs without assistance 3 Moderate disability; requiring some help, but able to walk without assistance 4 Moderately severe disability; unable to walk without assistance and unable to attend to own bodily needs without assistance 5 Severe disability; bedridden, incontinent and requiring constant nursing care and attention 6 Dead
NIHSS	National Institute of Health Stroke Scale	Method for quantifying neurologic deficits developed by the National Institutes of Health. It is used to assess the severity of a stroke.
PED	Pipeline Endovascular Device	Pipeline Endovascular Device

Abbreviation	Abbreviated Term	Definition
Primary Efficacy Endpoint	Complete aneurysm occlusion (defined as Raymond-Roy grade 1 ⁵⁵) without significant parent artery stenosis (\leq 50%) or retreatment of the target aneurysm 1-year post-procedure	The primary effectiveness endpoint assessed by: 
• Occlusion status: by a 3-member adjudicated read by the imaging Core Laboratory according to the Scale of Roy• Parent Artery stenosis: by the 3-member adjudicated read by the imaging Core Laboratory.• Retreatment: by the investigator reported events of retreatment.

Abbreviation	Abbreviated Term	Definition

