Subjects will be considered enrolled in the study once the patient has signed and dated the Informed Consent or DRF and the Pipeline™ Flex Embolization Device with Shield Technology™ is advanced into the micro catheter inside the patient. All enrolled subjects who underwent the study procedure and in whom an attempt to implant the device was made will be included in the analysis population.

A CEC will be in place for the study using a minimum of three physicians knowledgeable in the appropriate disciplines and medical specialties pertinent to the disease state being evaluated in this clinical study. This committee will be responsible for the review and adjudication to the study variables of all events identified in the CEC Charter/Manual of Operations.

The CEC will independently adjudicate to specified endpoint event definitions, event relatedness, event severity, and event outcomes.

The imaging core laboratory will be responsible for the qualitative image analysis to determine aneurysm occlusion, parent artery stenosis, and device migration. An imaging protocol will be provided to the site.

Pre-Specified Study Endpoints:

The pre-specified study endpoints and analysis listed here are the primary body of data that will be collected, analyzed, and summarized in a series of tables, lists, and graphs as part of the final report for this study. Other analysis will be conducted as part of the final report but these are the core set of analyses that will constitute the foundation of the clinical study report.

Primary endpoints:

Safety:

- Occurrence of major stroke in the territory supplied by the treated artery or neurological death post-procedure (1-year)

Effectiveness:

- Complete aneurysm occlusion (defined as Raymond-Roy grade 1) without significant parent artery stenosis ($\leq 50\%$) or retreatment of the target aneurysm post-procedure (1-year)

Secondary endpoints:

Safety:

- Occurrence of major stroke in the territory supplied by the treated artery or neurological death at 30 days post-procedure due to procedural complications
- Delayed intracerebral hemorrhage > 30 days post-procedure

Effectiveness:

- Device deployment success rate at the target site

Additional Safety Analyses:

- [REDACTED]
- [REDACTED]

- [REDACTED]
 - [REDACTED]
 - [REDACTED]

Additional Effectiveness Analyses:

- [REDACTED]
 - [REDACTED]
 - [REDACTED]
- [REDACTED]
- [REDACTED]
- [REDACTED]
- [REDACTED]
- [REDACTED]

Study Procedure:

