In all cases, primary effectiveness will be defined according to the angiographic core laboratory's adjudication of images received.

Patient Accounting and study disposition

A complete accounting of patient participation in the study by analysis population will be presented in Table 14.1.1a entitled *Patient Accounting*. The purpose of this table is to provide an accounting of subjects from their entrance into the study through the final visit and to account for the evaluations of subjects in the analyses of efficacy and safety, including reasons for early study termination. The table will display the number of subjects that were consented and the number and percentage of subjects from the ITT, FAS, ICA, and non-ICA populations that:

- Underwent the study procedure (n/%)
- Evaluated at the 30-day follow-up visit (n/%)
- Evaluated at the 90-day follow-up visit (n/%)

- Evaluated at the 180-day follow-up visit (n/%)
- Evaluated at the 1-year follow-up visit (n/%)

The final study disposition of all subjects participating in the study by analysis population will be presented in Table form entitled *Patient Final Study Disposition*. A table entitled *Patient Accounting by Investigational Site* will follow a similar format and method of tabulation; however, this table will be presented by investigation site. A table entitled *Reasons for Screen/Implant Failures* will contain a tabulation of the number of subjects classified as screen/implant failures by individual reason.

A table entitled *Summary of Protocol Deviations* will contain a tabulation of the number and percentage of subjects from the ITT population with a deviation by deviation code. Multiple deviations per patient within the same category will only be counted once.

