7.13.3 Post-Procedure Analyses

The first series of **Post-Procedure** analyses to be summarized will address the outcomes after the procedure. Within this series, there are 9 separate parameters:

- Aneurysm occlusion (Class 1: Complete obliteration, Class 2: Residual neck, or Class 3: Residual Aneurysm), derived from the post-procedure imaging adjudicated by Core Lab.
- Modified Rankin Scale (mRS); a multinomial endpoint that comes directly from the site reported case report form for evaluating the intra-patient over time and the change from baseline. The mRS will be scored for each patient by an evaluator at the clinical site. The mRS is a well-accepted and defined scoring system for measuring the degree of disability or dependence in the daily activities of people who have suffered a stroke using a multinomial ordinal scale:
 - 0 No symptoms at all
 - 1 No significant disability despite symptoms; able to carry out all usual duties and activities
 - 2 Slight disability; unable to carry out all previous activities, but able to look after own affairs without assistance

The mRS score at 1 year will be dichotomized (>2 vs. ≤ 2) and summarized using counts, percentages, and 2-sided 95% exact binomial confidence intervals.

- NIH Stroke Scale (NIHSS); a continuous endpoint that comes directly from the site reported clinical case report form for evaluating the intra-patient over time and the change from baseline. The NIHSS is a 15-item neurologic examination stroke scale used to evaluate the effect of acute cerebral infarction on the levels of consciousness, language, neglect, visual-field loss, extraocular movement, motor strength, ataxia, dysarthria, and sensory loss.
- Platelet reactivity testing, based on the VerifyNow, VASP, MEA, TEG, LTA testing reported as a percentage. A continuous endpoint that comes directly from the site reported clinical case report form.
- Change in antiplatelet therapy because of the platelet reactivity testing; a binary variable and comes directly from the site reported clinical case report form.
- Retreatment of the target aneurysm; a binary variable adjudicated by the imaging core laboratory. The recurrence of the aneurysm will be summarized using the percentage of subjects that experience aneurysm recurrence. Aneurysm recurrence is defined as an aneurysm that achieves complete occlusion at 6 months post-procedure, and then is no

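### The SAP gives two sources for retreatment, a failure component of primary effectiveness: investigator reports in section 2, core-laboratory adjudication in 7.13.3

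*SAP*

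**What the plan says.** SAP sections 5 and 7.9 define primary effectiveness by three conditions on the target aneurysm at 1 year: Raymond-Roy grade 1, parent artery stenosis of at most 50%, and no retreatment. Three places bear on where the third condition comes from.

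- **SAP section 2, Primary Efficacy Endpoint.** Occlusion and stenosis come from a three-member core-laboratory read. The third component has its own source: "Retreatment: by the investigator reported events of retreatment".
- **SAP 7.13.3, Post-Procedure Analyses.** The same variable is listed as "Retreatment of the target aneurysm; a binary variable adjudicated by the imaging core laboratory".
- **SAP 7.4, Imputation of Outcome Data.** After the rules for choosing the endpoint image, the section closes: "In all cases, primary effectiveness will be defined according to the angiographic core laboratory's adjudication of images received".

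The core laboratory's remit is set out twice. SAP section 5 gives it as "qualitative image analysis to determine aneurysm occlusion, parent artery stenosis, and device migration". Protocol 8.2 gives it as "aneurysm characteristics, side branch coverage by the Pipeline device, aneurysm occlusion, parent artery stenosis, and device migration". Neither list contains retreatment. Protocol section 21 defines retreatment as "Any subsequent intervention (post study procedure with Pipeline implant) performed to treat the target IA".

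**The concern.** One component of the primary endpoint has two named sources, and no rule says which prevails. Two programmers could each follow the SAP and classify the same subject differently. The stand-alone retreatment rate and the retreatment component of the primary endpoint could also disagree within one report.

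The two sources are not equivalent. Retreatment is a procedure that was performed. An image reader knows of it only if it shows on the images received or the reader is told. SAP section 5 allows retreatment at any time at the investigator's discretion. SAP 7.4 says follow-up imaging was done per standard of care and not required at each visit. Its selection rule takes the last adjudicated image from day 141 (with a modality preference) and is silent on retreatment before that image. The image used can therefore postdate a second intervention and show its result.

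For retreatments that sites report but the core laboratory does not register, the error can go only one way: a failure becomes a success.

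**Working it through.** **1. The sources side by side**

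| Place | Occlusion | Stenosis | Retreatment |
|---|---|---|---|
| SAP section 2 | Core laboratory | Core laboratory | Investigator report |
| SAP 7.13.3 | Core laboratory | Core laboratory | Core laboratory (explicit) |
| SAP 7.4, closing sentence | Core laboratory | Core laboratory | Not named; covered only as part of primary effectiveness |
| Core-laboratory remit (SAP section 5, Protocol 8.2) | Listed | Listed | Not listed |

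The explicit contradiction is between section 2 and 7.13.3. The data collection agrees with section 2: Protocol Table 5-1 lists retreatment as a follow-up item, and the SAP schedule of assessments has an entry for a retreatment procedure.

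**2. A subject on whom the sources differ**

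Take a target aneurysm that is retreated within the year. The site reports it, the core laboratory does not register it, and the last image from day 141 shows Roy class 1 with stenosis of 50% or less. Under section 2 the subject is a failure. Under 7.13.3 the subject is a success.

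**3. Size per subject**

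The plan states no figure on this point to reproduce. SAP section 5 intends 200 attempted deployments, and SAP 7.7 counts one target aneurysm per patient. One misclassified subject shifts the rate by 1/200 = 0.5 percentage point.

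**4. Effect on the comparison with 50%**

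SAP section 6 sets a 50% threshold for effectiveness (that sentence does not itself mention retreatment) and two-sided 95% Clopper-Pearson limits. The lower limit for x successes in n is the 2.5% quantile of a Beta(x, n − x + 1) distribution. With n = 200:

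- x = 115 (57.5%): Beta(115, 86), lower limit 50.3%.
- x = 114 (57.0%): Beta(114, 87), lower limit 49.8%.

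So 115 successes is the smallest count whose lower limit exceeds 50%.

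The next table is an illustration. The apparent success counts and the numbers reclassified are assumptions, with the latter running from 1% to 10% of N. Cells show the lower 95% limit after reclassification.

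| Apparent successes | 0 moved | 2 moved | 6 moved | 10 moved | 20 moved |
|---|---|---|---|---|---|
| 120 (60%) | 52.9% | 51.8% | 49.8% | 47.8% | 42.9% |
| 136 (68%) | 61.1% | 60.0% | 58.0% | 55.9% | 50.8% |
| 150 (75%) | 68.4% | 67.3% | 65.2% | 63.1% | 58.0% |

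At 60%, moving 6 subjects (120 − 6 = 114) brings the lower limit below 50%. At 68% or 75%, moving 20 does not.

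**The case against.** The strongest reply is that section 2 already settles the matter. It defines the primary endpoint and assigns a source to each component. The sentence in 7.13.3 sits under analyses additional to the protocol and describes a stand-alone variable. It also reads like a drafting slip: the same bullet runs retreatment together with core-laboratory recurrence, and major stroke follows without a break. The 7.4 sentence closes the image-selection rules, and its natural meaning is that the core laboratory's reading of an image prevails over the site's.

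Much of this stands. A reader might infer that the SAP twice states that retreatment is core-laboratory adjudicated. It does so explicitly only once; 7.4 never names retreatment. A reader might also infer that retreated subjects are usually graded on an image taken after retreatment, or that the laboratory will often miss a retreatment. The documents support neither: they say nothing about how often this occurs, and they ask for all imaging to be sent to the core laboratory, which makes a missed retreatment less likely.

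The reply does not remove the contradiction. Nothing says that section 2 overrides 7.13.3. The 7.4 sentence lies in the derivation of primary effectiveness and makes no exception. Sending all images also does not say which source governs when the image record and the site's report differ.

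**Conclusion.** The inconsistency between SAP section 2 and 7.13.3 is real, and 7.4 leaves it open by implication. It should be corrected because it concerns a component of the primary endpoint and would favour the device if resolved the wrong way.

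The harm is conditional. It requires that the core-laboratory source be used, that the laboratory not register a retreatment, and that the selected image otherwise meet the success criteria. The documents do not show that this will happen.

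It is tempting to put a size on the overstatement. Assuming 3–5% retreated (6 to 10 of 200) and half of them unseen gives 3/200 to 5/200, or 1.5 to 2.5 points. Both inputs are assumptions without a source, and the result is a maximum even on those inputs, because it treats every unseen case as an otherwise complete success. What the documents support is 0.5 point per misclassified subject at N = 200.

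Nor do they support a claim that the conclusion would be overturned. The comparison with 50% turns between 114 and 115 successes, so it changes only for a rate near 57%. Earlier Pipeline results in Protocol 1.2.3 lie higher: 73.6% at 180 days for occlusion without major stenosis, and 86.8% at one year and 75% at last visit for occlusion alone. Those endpoints and populations differ from this study's. There is also no formal success criterion.

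**What to change.** Make these changes to the SAP wording:

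1. In 7.13.3, take retreatment of the target aneurysm from the investigator-reported retreatment eCRF, as section 2 does.
2. In 7.4, limit the closing sentence on core-laboratory adjudication to occlusion and stenosis.
3. In sections 2 and 7.4, state that any investigator-reported retreatment of the target aneurysm within the 1-year endpoint period, or before the image used if that image is later, is a failure whatever the image shows. State the day on which that period ends, since the 1-year visit has a window of 8 weeks either side.
4. State that a subject with such a retreatment and no qualifying image is counted as a failure and is not multiply imputed.

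The cut-off in item 3 should not be the image date alone. A subject imaged at day 160 with complete occlusion and retreated at day 300 would then pass a 1-year endpoint that requires no retreatment. A subject without a qualifying image would have no cut-off at all.

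The cost is SAP text and a small change to the endpoint derivation. The retreatment data are already collected. The reported success rate may be slightly lower.

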9.4 Analysis of Baseline Demographics and Procedural Characteristics

Descriptive statistics will be generated for pre-intervention demographics, aneurysm characteristics and procedural characteristics, device usage and adverse events. Categorical variables will be analyzed using frequency, incidence, and event rate. For continuous variables collected in the study, analysis will include mean, median, standard deviation, and range.

The following data points will be analyzed in this study:

- Antiplatelet therapy regimen
- Adverse events related to antiplatelet therapy
- Platelet reactivity testing results
- Moderate and Severe bleeding events utilizing GUSTO criteria
- All intracranial hemorrhages and delayed intracranial hemorrhages (>30 days post-procedure)
- Index procedure time
- Number of Pipeline™ Flex Embolization Device with Shield Technology™ utilized
- Device deployment success rate at target site
- Aneurysm occlusion at 6 months, 1 year and at last follow-up
- Recurrence and retreatment rates at 1 year post-procedure and at last follow-up

- The composite percentage of patients with modified Rankin Scale of 0-2 or no change from baseline at 1 year and at last follow-up.
- Occurrence of major stroke in the territory supplied by the treated artery or neurological death.

Major Stroke events will be further characterized based on whether:

- Event was caused by thromboembolic events
- Event was caused by side-branch occlusion due to the study device

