The study population will consist of patients who have an intracranial aneurysm and qualify for enrollment into the study. The treated aneurysm may be ruptured (with a Hunt and Hess grade of ≤ 3); under these clinical conditions, Pipeline™ Flex Embolization Device with Shield Technology™ may be used according to the Instructions for Use and the intended use statement during the treatment regimen. The term Primary Study Procedure refers to the initial study procedure and is used consistently to discriminate between the primary study procedure and re-treatment of the target aneurysm. If more than one aneurysm can be covered by a single Pipeline device or two overlapped devices, the multiple aneurysms treated by that device(s) may all be included in the study. If the patient has more than one aneurysm and all aneurysms requiring treatment cannot be covered by a single Pipeline device or two overlapped devices, the non-target aneurysms should be treated first. After waiting at least 30 days, the patient may return for treatment of the target aneurysm with the Pipeline™ Flex Embolization Device with Shield Technology™.

The maximum number of subjects to be enrolled in this clinical investigation is 200. The maximum number of sites permitted to participate in this clinical investigation is 25 with no more than 30 subjects enrolled per site.

All images taken of the aneurysm (e.g., angiograms, CT, MR, rotational angiography with 3D reconstruction, cone beam CT, etc.) will be sent to the Independent Core Lab designated for this clinical investigation for adjudication.

The planned analyses identified in this statistical analysis plan (SAP) may be included in regulatory submissions and/or future manuscripts. Exploratory analyses, not identified in this SAP, may be performed to support the clinical development program. Any post-hoc, or unplanned, analyses that are performed but not identified in this SAP will be clearly identified in the CSR. The structure and content

of this SAP provides sufficient detail to meet the requirements identified by the FDA and International Conference on Harmonization of Technical Requirements for Registration of Pharmaceuticals for Human Use (ICH): Guidance on Statistical Principles in Clinical Trials.

This statistical analysis plan (SAP) is based on revision B of the protocol dated 24-Jun-2016.

4. Study Objectives

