7.9 Evaluation of Objectives

As previously described, the primary objective of this study is to assess the *outcomes* of the Pipeline™ Flex Embolization Device with Shield Technology™ in patients undergoing treatment for intracranial aneurysms in a large real-world, post-market setting. *Outcomes* will be assessed based on a series of standardized measurements recorded during the procedure and during the post-procedure follow-up period.

The Intent to Treat (ITT) will be considered the primary population, but not limited to, in the analysis of data for this study. When analyzing an outcome within a population, missing data will be reflected as the function of the denominator reported (xx.x% n/N) while the population number will remain constant. [i.e. ITT n=200 outcome Y (50%, 98/196)]

The pre-specified study endpoints and analysis listed here are the primary body of data that will be collected, analyzed, and summarized in a series of tables, lists, and graphs as part of the final report for this study. Other analysis will be conducted as part of the final report but these are the core set of analyses that will constitute the foundation of the clinical study report.

Primary endpoints:

Safety:

- Occurrence of major stroke in the territory supplied by the treated artery or neurological death post-procedure (1-year)

Effectiveness:

- Complete aneurysm occlusion (defined as Raymond-Roy grade 1) without significant parent artery stenosis ($\leq 50\%$) or retreatment of the target aneurysm post-procedure (1-year)

Secondary endpoints:

Safety:

- Occurrence of major stroke in the territory supplied by the treated artery or neurological death at 30 days post-procedure due to procedural complications
- Delayed intracerebral hemorrhage > 30 days post-procedure

Effectiveness:

- Device deployment success rate at the target site

Analysis for primary effectiveness endpoint interaction of site homogeneity and poolability testing will be conducted and reported.

Analysis of primary effectiveness endpoint by:

- Missing Data by Worst Case Scenario
- Aneurysm Location (with observed data)
- Aneurysm Location by Artery Segments (ITT population with observed data)
- By age (ITT and FAS population with observed data)

Analysis for primary effectiveness endpoint tipping point for incidence of complete target aneurysm occlusion at 1 year post procedure (ITT population)

CEC event of interest through 1 year will be reported for:

- GUSTO Bleeding
- Procedural:

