longer completely occluded, based on Core Lab, (i.e., residual neck or residual aneurysm is found by Core Lab) at 12 months post-procedure. This endpoint will only be defined in those subjects with both 6- and 12-month imaging adjudicated. The percentage of subjects that undergo retreatment of the target aneurysm after the initial PED treatment will also be presented. Major stroke in the territory supplied by the treated artery or neurological death at 30 days post-procedure due to procedural complications; the event and event-relatedness will be adjudicated by the CEC. The 1-year event rate will also be tabulated and reported. A binary variable, and the event will be adjudicated by the CEC.

- Intracerebral hemorrhage (ICH) > 30 days post-procedure; the event will be adjudicated by the CEC. The 1-year event rate will also be tabulated and reported. A binary variable, and the event will be adjudicated by the CEC.
- Parent artery stenosis; continuous variable from the post-procedure imaging adjudicated by Core Lab, dichotomized into >50% and ≤50% stenosis. Additionally, stenosis will be presented by quartile.
- Device migration; a categorical variable from the post-procedure imaging adjudicated by Core Lab.

The second series of **Post-Procedure** variables to be summarized will address the safety and efficacy profile over the course of the entire clinical investigation.

- The device-related neurologic adverse event rate at 1 year post-procedure will be presented with the relationship between the device and the neurologic adverse events adjudicated by the independent CEC. Disabling stroke or neurological death at 1 year (as observed)
- Ischemic and Hemorrhagic Cerebrovascular Events (as adjudicated by CEC) : includes incidence of Stroke (Major or Minor, Ipsilateral or Contralateral), Cerebral Infarction (Symptomatic or Asymptomatic), Intracranial Hemorrhage, Transient Ischemic Attack, and Target Aneurysm Rupture
- Aneurysm recurrence
- Device Related Serious Adverse Events
- Procedure related Serious Adverse Events

8. Validation Requirements

Output will be validated by level I or II validation.

Level I: The peer reviewer independently programs output and then compares the output with that generated by the original Statistical Programmer.

Level II: The peer reviewer reviews the code; where appropriate, performs manual calculations or simple programming checks to verify the output.

9. References

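### The recurrence rate in SAP 7.13.3 is not limited to subjects completely occluded at 6 months, so a plain reading dilutes it by subjects who cannot have the event

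*SAP*

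**What the plan says.** SAP 7.13.3 gives the summary measure: "The recurrence of the aneurysm will be summarized using the percentage of subjects that experience aneurysm recurrence". The event has two parts. The first is that "Aneurysm recurrence is defined as an aneurysm that achieves complete occlusion at 6 months post-procedure". The second is that the Core Lab finds a residual neck or residual aneurysm at 12 months. One sentence then sets who can be evaluated: "This endpoint will only be defined in those subjects with both 6- and 12-month imaging adjudicated". It does not mention occlusion status at 6 months.

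Two other places bear on the denominator. SAP 7.9 gives a general convention, that "missing data will be reflected as the function of the denominator reported". Protocol 9.4 lists "Recurrence and retreatment rates at 1 year post-procedure and at last follow-up" among the data to be analysed, as does Protocol 3.1; neither gives a denominator. Nothing else in either document limits recurrence to subjects who were completely occluded at 6 months.

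**The concern.** A subject whose aneurysm is not completely occluded at 6 months cannot meet the recurrence definition. If that subject has both images, the evaluability sentence lets the subject in, and the subject counts as a non-recurrence. The percentage then combines two things: how often the device achieves occlusion by 6 months, and how often that occlusion is lost by 12 months. A reader will take a recurrence rate to mean the second.

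This matters mainly for comparison. SAP Section 3 says the results will be contrasted with studies of the Pipeline device without the surface treatment and will support a US indication evaluation. A rate that carries p6 inside it cannot be compared fairly across studies with different early occlusion. Recurrence is also listed in Protocol 3.1 and 9.4, and SAP 7.13.3 includes it in the safety and efficacy profile for the whole study.

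**Working it through.** The documents state no recurrence rate, sample size or precision for this outcome, so there is no planned figure to reproduce.

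**Identity.** Let x be the number of recurrences, N the subjects with both adjudicated images, M the subset completely occluded at 6 months, and p6 = M/N. All x events fall within M, so

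x/N = (x/M) × p6.

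The relative understatement is 1 − p6, and the at-risk rate is the as-written rate multiplied by 1/p6.

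**Inputs for p6.** This study's own p6 is unknown, so the Protocol's figures for the earlier device serve as proxies:

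- Protocol 1.2.3, single-arm trial in large and giant aneurysms: 78/106 = 73.6% at 180 days. This is a composite that also requires no major stenosis.
- Protocol 1.2.3, prospective post-market registry: 77/103 = 74.8% (stated as 75%). This is occlusion at the last visit, in subjects with at least 6 months of imaging follow-up (median 7.8 months).
- Protocol 1.2.3, first prospective multicenter trial: 28/30 = 93.3% at 180 days. This is the only plain 180-day complete occlusion figure, and it comes from a small study.
- Protocol 1.2.2, range across studies: 68% to 94.4%, not fixed to 6 months.

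**Result**, with at-risk recurrence assumed to be 5%:

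| p6 | 1 − p6 | 1/p6 | Reported rate (5% × p6) | Shortfall, points |
|---|---|---|---|---|
| 68% | 32% | 1.47 | 3.4% | 1.6 |
| 73.6% | 26% | 1.36 | 3.7% | 1.3 |
| 74.8% | 25% | 1.34 | 3.7% | 1.3 |
| 93.3% | 7% | 1.07 | 4.7% | 0.3 |
| 94.4% | 6% | 1.06 | 4.7% | 0.3 |

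**Intervals.** SAP Section 6 uses two-sided 95% Clopper-Pearson limits for dichotomous device outcomes. Assume N = 150 and p6 = 73.6%, so M = 150 × 0.736 ≈ 110.

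- 5 recurrences: 5/150 = 3.3% (1.1% to 7.6%) as written; 5/110 = 4.5% (1.5% to 10.3%) among those at risk.
- 0 recurrences: the upper limit is 1 − 0.025^(1/n), which is 2.4% for n = 150 and 3.3% for n = 110. The point estimate is 0% either way.

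**Comparison across studies (assumed rates).** At-risk recurrence of 10% with p6 = 68% is reported as 6.8%. At-risk recurrence of 8% with p6 = 94.4% is reported as 0.08 × 0.944 = 7.6%. The less durable result shows the lower figure.

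**The case against.** The strongest reply is that the sentence states a necessary condition. It says both images must exist, not that every subject with both images is counted, and the word denominator does not appear. Because complete occlusion at 6 months is in the event definition, a programmer could infer an at-risk denominator. That is fair, and it means the text does not prove that the diluted rate will be produced. But this is the only sentence that sets the evaluable set, and it names imaging alone. The convention in SAP 7.9 addresses missing data and gives no rule for an endpoint conditional on earlier status. If two readings are open, two independent programmers under the Level I check in SAP Section 8 could report different rates from the same data.

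A second reply is that recurrence over all evaluable subjects is a legitimate unconditional incidence. It is, but the SAP does not say that this is the quantity intended, and the incidence cannot be read as durability without p6 beside it.

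A third reply is that poor early occlusion would be visible elsewhere. This stands in part. SAP 7.7 tabulates occlusion class by visit, and the primary effectiveness endpoint depends on complete occlusion. Patient listings should allow the at-risk count to be recovered, but the SAP does not commit to reporting it.

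Three stronger readings are tempting and are not supported:

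- A reader might infer that the rate is understated by a flat one quarter. That uses only the 73.6% and 74.8% proxies, neither of which is a plain 6-month occlusion rate, and leaves out 93.3%.
- A reader might infer that a less effective device necessarily shows lower recurrence. That holds only if at-risk recurrence stays the same as p6 falls, which the documents do not establish.
- A reader might infer that a main conclusion is at risk. Recurrence is not among the listed primary or secondary endpoints, and SAP Section 6 sets thresholds only for the safety composite and for occlusion without significant stenosis.

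**Conclusion.** The point holds as a modest defect in a descriptive outcome. On the plain reading of SAP 7.13.3, the recurrence rate is the at-risk rate multiplied by p6. The relative understatement is 6% to 32% over the documents' occlusion range. The absolute effect is about 0.3 to 1.6 points, and that depends on the assumed 5% at-risk recurrence.

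The effect on the point estimate may be nil: Protocol 1.2.3 reports no recurrences in the trial in large and giant aneurysms, and a zero count here would change only the upper limit. The p6 values come from the earlier device. The number of subjects with both images cannot be forecast, because follow-up imaging is optional in the SAP's Schedule of Assessments. No primary conclusion changes. What is affected is the planned contrast with other Pipeline studies, where the diluted rate would mix early occlusion failure with durability, never to the device's disadvantage.

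**What to change.** Replace the evaluability sentence in SAP 7.13.3 with one stating that the denominator is subjects whose target aneurysm was adjudicated by the Core Lab as completely occluded at 6 months and who have an adjudicated 12-month image. Report that number with the rate and its exact (Clopper-Pearson) 95% confidence interval.

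The cost is one sentence and no new data. The denominator is smaller, the interval wider, and the rate slightly higher whenever any recurrence is seen.
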